3.5. Method of Assigning Subjects to Treatment Groups

This is an open-label study.

3.6. Blinding and Unblinding

This is an open-label study.

[figure not shown]
3.7. Schedule of Events

Please see protocol INCB 18424-902, An Open-Label, Single-Arm, Phase 4 Study of Ruxolitinib Cream in Adults with Atopic Dermatitis Experiencing Sleep Disturbance in the United States

^b PROMIS Sleep Disturbance – Short Form 8b questionnaire.

^c As measured by Ōura Ring wearable device during the screening sleep assessment (which is separate from the pretreatment sleep assessment).

^h Continuous treatment with ruxolitinib cream 1.5% twice a day of all areas identified at baseline, regardless of lesion clearance; new and/or expanded areas of AD may also be treated but not in excess of a total of 20% BSA.

(Morpheus) for a detailed schedule of events.

4. Statistical Analysis and Reporting

The final study analysis will be conducted only after all subjects have completed the study as described in the referenced protocol, a thorough review of all collected data has been conducted and approved, and a final SAP has been approved and signed prior to locking of the final data.

4.1. Introduction

Data processing, tabulation of descriptive statistics, calculation of inferential statistics, and graphical representations will primarily use SAS (release 9.4 or higher). If the use of other software is warranted, the final statistical methodology report will detail what software was used for what purposes.

Continuous (quantitative) variable summaries will include the number of subjects (n) with non-missing values, mean, standard deviation (SD), median, minimum, and maximum. The minimum and maximum will be reported with the same degree of precision (i.e., the same number of decimal places) as the observed data. Measures of location (mean and median) will be reported to 1 degree of precision more than the observed data and measures of spread (SD) will be reported to 2 degrees of precision more than the observed data.

Categorical (qualitative) variable summaries will include the frequency and percentage of subjects who are in the particular category or each possible value. In general, the denominator for the percentage calculation will be based upon the total number of subjects in the study population unless otherwise specified. The denominator for by-visit displays will be the number of subjects in the relevant study population with non-missing data at each visit. Percentages will be presented to 1 decimal place. Counts of zero will be presented without percentages.

Unless otherwise indicated, all statistical tests will be conducted at the 0.05 significance level usin 2-tailed tests, and p values will be reported. Corresponding 95% confidence intervals (CIs) will be presented for statistical tests. All p values will be displayed in four decimals and rounded using standard scientific notation (e.g. 0.XXXX). If a p value less than 0.0001 occurs it will be shown in tales as <0.0001; similarly, if a p value greater than 0.9999 occurs, it will be shown in tables as >0.9999. Confidence intervals will be reported to 1 degree of precision more than the observed data.

4.2. Interim Analysis and Data Monitoring

No interim analyses or data monitoring are planned.

5. Analysis Populations

The following analysis populations are planned for this study:

• Intent-To-Treat Population (ITT): The ITT population includes all subjects who enrolled in the study.

- Safety Population (SAF): The Safety Population includes all subjects who received at least 1 application of study drug during the treatment period.
- **Per Protocol (PP)**: The PP Population includes all subjects who have no important protocol deviations.

Assignment of subjects to populations will be confirmed at a data review to be held before the study database is locked.

6. General Issues for Statistical Analysis

6.1. Statistical Definitions and Algorithms

6.1.1. Baseline

For the following endpoint variables, calculations of change from baseline to Week 8 in sleep data, baseline comprises the 7-day average prior to the first dose: TST, PROMIS 8b. See Section 6.1.7 for details.

Otherwise, for non-sleep data, the last observation recorded on or before the first dose of treatment will be used as the baseline value.

6.1.2. Adjustments for Covariates

There will be no adjustments for covariates in any of the analyses.

6.1.3. Multiple Comparisons

For the primary efficacy endpoint, differences will be assessed at alpha = 0.05. No adjustments will be made for multiple comparisons for other secondary/exporatory endpoints.

[figure not shown]
6.1.4. Handling of Dropouts or Missing Data

See Section 6.1.7 for details regarding missing PROMIS score and 6.1.8 for details regarding missing AE date data handling conventions.

6.1.5. Analysis Visit Windows

For all analyses, early termination and unscheduled visits will be assigned analysis visits according to the analysis windows in the following table. Where multiple measurements for a particular parameter appear within an analysis window, the result closest to the target day will be used. If equidistant, the latter result will be used for the summary measure. Though all measures may not be used in the data summaries, all measurements appear in the datasets and listings.

Scheduled Visit		Analysis	Analysis	s Window
(Subject Visit	Analysis Visit	Window Target	Lower Bound	Upper Bound
Window)		Day		11
Screening	Screening	NA		
Enrollment	Day 1	1		1

(Day 1)				
Visit 2 (Week 4 ± 7 days)	Week 4	28	2	55
Visit 3 (Week 8 + 7 days)	Week 8	56	56	63
Follow-Up (30 Days Post Visit 3 + 7 days)	Follow-Up	86	64	NA

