#### **Treatment Groups and Duration:**

This is a Phase 4, multicenter, open-label, single-arm study to evaluate the reduction in sleep disturbance among participants with AD after treatment with ruxolitinib cream. This study will enroll approximately 100 adults ( $\geq 18$  years of age) with at least mild severity AD who have sleep disturbance. Individuals with known sleep-related conditions that are not associated with their AD diagnosis will be excluded from the study.

A minimally invasive wearable device (Ōura Ring) and a will be used to collect objective measures of sleep during the study. The Ōura Ring will be used during a 7-day screening sleep assessment (to determine study eligibility), and both technologies will be used during a 7-day pretreatment sleep assessment (to further determine eligibility and to establish baseline sleep patterns) as well as throughout the 8-week treatment period (to monitor postbaseline sleep patterns).

All participants will apply ruxolitinib cream at the FDA-approved strength (1.5%) BID over the 8-week treatment period, during which participants will treat all baseline AD lesions BID, regardless of whether or not the lesion(s) improve. New and/or expanded areas of AD may also be treated but not in excess of a total of 20% BSA (for original plus new areas) per application.

All participants will have follow-up assessments 30 (+ 7) days after the end of treatment (Week 8/EOT or ET) to evaluate safety.

**Table 3:** Schedule of Activities

	Screening Perioda		Treatment Period			Safety Follow-Up Period	
Visit Day (Range)/ Visit Week	Days -42 to -7	Days -7 to -1	Day 1/ Baseline	Week 4 (± 7 days)	Week 8 (+ 7 days)/ EOT/ET	30 (+ 7) Days after Last Application	Notes
Administrative Procedures							
Informed consent	X						Section 8.1.1
Inclusion/exclusion criteria	X		X*				*Reassess applicable inclusion/exclusion criteria; Section 5
Demography and general medical history	X						Section 8.1.5.1
Relevant medical and treatment history	X						Section 8.1.5.2
Prior/concomitant medications	X		X	X	X	X	Section 6.6
Contact IRT	X		X	X	X		Section 8.1.3
Ōura Ring wearable device set-up	X						
eDiary set-up	X						Set-up includes giving participants access to the eDiary; Section 8.1.4
Application of study drug BID			X	X	X		First application occurs on Day 1 at the site under direct site staff supervision; subsequent applications are at home; applications are recorded in the eDiary; Section 6.1

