9.2. Clinical Laboratory Evaluations

[figure not shown]
Laboratory test results will be summarized descriptively by time point as both observed values and change from baseline values.

The number of subjects with clinical laboratory values below, within, or above the normal range by time point and in relation to baseline will be tabulated for each clinical laboratory analyte by treatment group (shift table).

Central Labs' normal ranges are provided from the Lab Vendor Q2 within the data transfer. Any local labs performed will utilize the local lab ranges input from the site into the EDC.

Lab Units will be standardized and displayed as follows:

Analyte Name	Unit
ALT	U/L
Albumin	g/L
Alkaline Phosphatase	U/L
AST	IU/L
Basophils	10^9/L
Basophils/Leukocytes	%
Bicarbonate	mmol/L
Direct Bilirubin	μmol/L
Total Bilirubin	μmol/L
Blood Urea Nitrogen	mmol/L
Calcium	mmol/L
Chloride	mmol/L
HCG	Positive/Negative
Creatinine	μmol/L
Eosinophils	10^9/L
Eosinophils/Leukocytes	%
Ery. Mean Corpuscular Volume	fL
Erythrocytes (RBC)	10^12/L
Erythrocytes Distribution Width (RDW)	%
FSH	IU/L
Glucose	mmol/L
HCT	Fraction of 1
HGB	g/L
HIV Screening	Reactive/Non-Reactive
Lactate Dehydrogenase	IU/L
Leukocytes (WBC)	10^9/L
Lymphocytes	10^9/L
Lymphocytes/Leukocytes	%
Mean Platelet Volume	fL

Monocytes	10^9/L
Monocytes/Leukocytes	%
Neutrophils	10^9/L
Neutrophils/Leukocytes	%
Phosphate	mmol/L
Platelets	10^9/L
Potassium	mmol/L
Protein	g/L
Sodium	mmol/L

Descriptive summaries of observed values and change from baseline will be presented for continuous hematology and chemistry for overall subjects at each study visit.

Laboratory values that are outside the normal range will be presented via a shift table and also be flagged in the data listings and presented with the corresponding normal ranges.

Serology tests including urinalysis, pregnancy, and HIV test results will be listed.

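### Every early-termination visit before Day 56 is assigned to Week 4, so early terminators' end-of-treatment labs, vital signs, IGA and %BSA are mislabelled or left out of the by-visit summaries

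*SAP*

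**What the plan says.** SAP 6.1.5 applies to all analyses. It says that "early termination and unscheduled visits will be assigned analysis visits according to the analysis windows in the following table". The table gives:

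- Week 4: target Day 28, Days 2 to 55
- Week 8: target Day 56, Days 56 to 63
- Follow-up: from Day 64

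The table has no EOT, ET or last-on-treatment analysis visit. When a window holds several results for a parameter, "the result closest to the target day will be used". For ties, "If equidistant, the latter result will be used for the summary measure". Unselected results are kept outside the summaries: "Though all measures may not be used in the data summaries, all measurements appear in the datasets and listings".

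The protocol groups ET differently. The visit column in Tables 3 and 4 reads "Week 8 (+ 7 days)/ EOT/ET", so ET shares its procedures with Week 8. Table 4 schedules chemistry and hematology at screening, in that shared column and at follow-up, with nothing at Week 4. IGA, %BSA and vital signs are scheduled at both Week 4 and Week 8/EOT/ET.

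On reporting, SAP 9.2 says "Laboratory test results will be summarized descriptively by time point as both observed values and change from baseline values" and adds shift tables by time point. SAP 9.3 summarizes vital signs at each visit. Tables 14.2.8 (%BSA) and 14.2.9 (IGA) are ITT summaries of change from baseline. Under SAP 4.1, by-visit denominators count only participants with data at that visit.

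**The concern.** For a participant who stops early, the ET visit is the end-of-treatment assessment. It is also the only scheduled on-treatment draw for chemistry and hematology. The window table separates that assessment from the Week 8/EOT results with which the protocol schedules it. Two things can follow:

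- **Omission.** Where a scheduled Week 4 result exists (vital signs, IGA, %BSA), the ET result competes with it for one place and usually loses.
- **Mislabelling.** Where no scheduled Week 4 result exists (chemistry, hematology, or a participant who stopped before Visit 2), the ET result appears as Week 4.

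Either way, the Week 8 rows for these parameters contain only participants seen on Days 56–63, and no other row collects the end-of-treatment status of the rest. Section 7.1.1 of the protocol requires discontinuation for, among other things, adverse events of unacceptable severity and AD that spreads beyond the treatable area. Some of the missing assessments could therefore be informative. The same section also lists device failure affecting sleep data on Days 49–56, so the protocol itself can produce ET visits just below the Day 56 bound.

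**Working it through.** **Inputs.** Windows, targets, closest-to-target rule and tie rule: SAP 6.1.5. Scheduled Week 4 visit: Day 28 ± 7, that is Days 21–35 (protocol Table 3). Laboratory schedule: protocol Table 4. Enrolled participants: 47 (SAP 3.2).

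**Step 1: where ET visits go.** ET days before the Week 8 window: 55 − 2 + 1 = 54. All 54 fall in Week 4 and none in Week 8. An ET visit on Days 56–63 does count as Week 8.

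**Step 2: which of these days are nearer Week 8.** The condition is |d − 56| < |d − 28|, which gives d > 42. Day 42 is equidistant (14 days each way). Days 43–55 are nearer Day 56: 55 − 43 + 1 = 13 days. On Day 55 the distances are 1 day to the Week 8 target and 27 days to the Week 4 target, yet the result is labelled Week 4.

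**Step 3: vital signs, IGA and %BSA when a scheduled Week 4 visit exists.** Let the scheduled visit be on day v and ET on a later day e ≤ 55. The ET result is summarized only if |e − 28| ≤ |v − 28|.

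| Week 4 visit | ET replaces the scheduled result | ET left out |
|---|---|---|
| Day 21 | Days 22–35 | Days 36–55 (20 days) |
| Day 24 | Days 25–32 | Days 33–55 (23 days) |
| Day 28 | none | Days 29–55 (27 days) |
| Day 32 | none | Days 33–55 (23 days) |
| Day 35 | none | Days 36–55 (20 days) |

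Over all v from 21 to 35 there are 34 + 33 + … + 20 = 405 day pairs. ET replaces the scheduled result in 14 + 12 + 10 + 8 + 6 + 4 + 2 = 56 (14%) and is left out in 405 − 56 = 349 (86%). This counts day pairs; it does not forecast how often it will happen. If the participant stops before Visit 2, the ET result is shown as Week 4.

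**Step 4: chemistry and hematology.** No Week 4 draw is scheduled, so there is no scheduled result to displace the ET value. Unless an unscheduled draw lies nearer Day 28, the ET value is summarized, but under Week 4. That row then holds only ET and unscheduled draws, while the Week 8 row lacks the ET draws that Table 4 groups with it.

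**Step 5: is there a rescue elsewhere?** SAP 6.1.4 refers only to missing PROMIS scores and AE dates. LOCF is specified only for TST (SAP 8.1.1). No other visible rule moves ET labs, vital signs, IGA or %BSA to an end-of-treatment summary.

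**Step 6: how many participants.** The documents give no count of ET visits. As an assumption, 5% of 47 is 2.35 and 30% is 14.1, so about 2 to 14.

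**The case against.** Allocating visits by actual study day is a usual convention. The Week 8 bounds mirror the protocol's one-sided visit window, and up to Day 41 the nearer target is indeed Day 28. The shared column in Table 3 says which procedures to perform; it does not say that an ET value estimates Week 8. Placing a Day 5 ET result in a Week 8 row would be an unstated carry-forward. All of this stands. It is the reason for keeping by-visit rows and adding a separate end-of-treatment row, rather than moving every ET visit into Week 8.

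Four stronger readings are tempting, and the documents do not support them:

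- **That all Week 8 tables describe completers only.** TST and PROMIS 8a have their own rules tied to Visit 3 (SAP 6.1.7.3 and 6.1.7.4). Table 14.2.1.1 carries early terminators' TST forward in the ITT population where a rolling average exists. The PROMIS 8b Week 8 derivation is not visible in the public text, so no effect on it can be claimed.
- **That ET safety data are lost.** ET labs are relabelled, not removed. All results stay in the datasets and listings, abnormal laboratory values have their own listing, and the TEAE tables are not windowed by visit.
- **That up to 14 of 47 would be missing from end-of-treatment tables.** The planning allowance from 100 to 70 covers loss to follow-up and device malfunction. Someone lost to follow-up may have no ET visit to misassign. Fourteen is only the top of an assumed range.
- **That the summaries are biased toward those who tolerated or responded.** Discontinuation reasons also include travel, disrupted sleep and device failure, and no frequencies are given.

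**Conclusion.** The point holds for windowed clinic and laboratory data. All 54 possible ET days before Day 56 map to Week 4, including 13 that are nearer Week 8. For vital signs, IGA and %BSA, such a result never reaches Week 8 and is usually displaced from Week 4 by the scheduled visit. For chemistry and hematology it appears at a time point where the protocol schedules no draw. On day proximity alone, the Week 4 label is wrong only for Days 43–55. For labs it departs from the Table 4 grouping throughout Days 2–55.

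The primary test and its sensitivity analysis do not change. The affected summaries are descriptive. With 47 enrolled, even 2 or 3 displaced or relabelled participants would be noticeable in a safety table, but their actual number and the direction of any bias are unknown. For IGA and %BSA, the conclusion assumes that no derivation withheld from the public SAP overrides 6.1.5. The change is worth making in the SAP.

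**What to change.** 1. In SAP 6.1.5, keep the by-visit rows. For ET and unscheduled visits, set the Week 4 upper bound at Day 42 and the Week 8 lower bound at Day 43.
2. Add a separate row, *End of treatment (last on-treatment value, including ET)*: for labs, including the shift tables, and vital signs in the Safety population; for IGA and %BSA in the ITT population. State that the ET visit qualifies even if it falls after the last application.
3. Footnote that any Week 4 laboratory entries come only from ET or unscheduled draws, and say how the new row corresponds to the protocol's Week 8/EOT/ET column.

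Both of the first two changes are needed. The new bounds alone move only 13 of the 54 days; the other 41 (Days 2–42) still go to Week 4, and only the added row captures them.

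The cost is two numbers in a table and one extra row in a few outputs, with no new data and no effect on the primary test. The downside is that the added row mixes treatment durations. A footnote can say so and give the range of study days. If the database is already locked, the row can be reported as post hoc, which SAP section 1 allows when it is identified as such.

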6.1.6. Pooling of Sites

[figure not shown]
No pooling will be done.

6.1.7. Derived Variables

6.1.7.1. General

- Age: Age will be calculated as the integer difference in years between the subject's year of informed consent and the year of birth.
- Change from baseline: The value at the target time point minus the value at baseline.
- Prior and concomitant medications: All medications taken prior to Screening or in the time interval between Screening and Enrollment/Visit 1 will be considered prior medications, whether or not they were stopped before Enrollment/Visit 1. Any medications continuing or starting after Enrollment/Baseline Visit will be considered concomitant. If a medication starts before enrollment and continues after enrollment it will be considered both prior and concomitant.
- **Study Day:** For analysis purposes, Study Day is calculated relative to the date of first dose of study drug. For study days on or after treatment start, study date = date treatment start date + 1. For study days before treatment start, study day = date treatment start date.
- Treatment-emergent adverse event (TEAE): Defined as 1) AEs with onset at the time of or following the start of treatment with IP through Week 8 (EOT) or 2) AEs starting prior to the start of treatment but increasing in severity or relationship at the time of, or following, the start of treatment with IP through Week 8 (EOT).

[figure not shown]

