#### **8.4.1.** Adverse Events

Adverse events will be monitored from the time the participant signs the ICF until at least 30 days after the last application of study drug. Adverse events that begin or worsen after informed consent should be recorded on the Adverse Events Form in the eCRF regardless of the assumption of a causal relationship with the study drug. Conditions that were already present at the time of informed consent should be recorded on the Medical History Form in the eCRF. Adverse events (including laboratory abnormalities that constitute AEs) should be described using a diagnosis whenever possible rather than by individual underlying signs and symptoms.

Adverse events will be reported by the participant (or, when appropriate, by a caregiver, surrogate, or the participant's legally authorized representative). The investigator and any qualified designees are responsible for detecting, documenting, and recording events that meet the definition of an AE or SAE and remain responsible for following up on AEs that are serious, that are considered related to the study drug/procedures, or that caused the participant to discontinue the study drug. Care will be taken not to introduce bias when detecting AEs and/or SAEs. Open-ended and nonleading verbal questioning of the participant, such as "How are you feeling?", is the preferred method to inquire about AE occurrences. Adverse events may also be detected when they are volunteered by the participant during the screening process or between visits or through physical examinations, laboratory tests, or other assessments. The definition, reporting, and recording requirements for AEs are described in Section 9.

All SAEs will be reported to the sponsor or designee within 24 hours. The investigator will submit any updated SAE data to the sponsor within 24 hours of it being available.

After the initial AE/SAE report, the investigator is required to proactively follow each participant at subsequent visits/contacts. All SAEs will be followed until resolution, stabilization, the event is otherwise explained, or the participant is lost to follow-up (as defined in Section 7.3).

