## 8.9. Follow-Up

## 8.9.1. Safety Follow-Up

The safety follow-up period is the interval between the EOT (Week 8) visit (or ET visit, if applicable) and the scheduled follow-up visit, which should occur 30 days after the EOT visit (or after the last dose of study drug if the EOT visit was not performed). Adverse events and SAEs must be reported up until at least 30 days after the last dose of study drug, the date of the

follow-up visit, or until toxicities resolve, return to baseline, or are deemed irreversible, whichever is longer. Reasonable efforts should be made to have the participant return for the follow-up visit and report any AEs that may occur during this period.

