#### Follow-Up of Adverse Events and Serious Adverse Events

- The investigator is obligated to perform or arrange for the conduct of supplemental measurements and/or evaluations as medically indicated or as requested by the sponsor to elucidate the nature and/or causality of the AE or SAE as fully as possible. This may include additional laboratory tests or investigations, histopathological examinations, or consultation with other health care professionals.
- Once an AE is detected, it should be followed in the Adverse Events Form in the eCRFs until it has resolved or until it is judged to be permanent; assessment should be made at each visit (or more

- frequently if necessary) of any changes in severity, the suspected relationship to the study drug, the interventions required to treat the event, and the outcome.
- When the severity of an AE changes over time for a reporting period (eg, between visits), each change in severity will be reported as a separate AE.
- If a participant dies during participation in the study or during a recognized follow-up period, the investigator will provide the sponsor with a copy of any postmortem findings, including histopathology.
- New or updated SAE information will be recorded in the originally completed eCRF and reported to Incyte Pharmacovigilance (either via email/fax if paper SAE form is used or in the SAE EDC CRF) until resolution, stabilization, the event is otherwise explained, or the participant is lost to follow-up.
- Any updated SAE data (including SAEs being downgraded to nonserious) will be submitted to the sponsor (or designee) within 24 hours of receipt of the information.

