#### 10.4.4. Exploratory Analysis

## 10.4.5. Safety Analyses

Safety analyses will be conducted for the safety population.

A TEAE is any AE either reported for the first time or worsening of a pre-existing event after first dose of study drug. Analysis of AEs will be limited to TEAEs, but data listings will include all AEs regardless of their timing to study drug administration. Adverse events will be tabulated by the MedDRA preferred term and system organ class. Severity of AEs will be based on the National Cancer Institute CTCAE v5.0 using Grades 1 through 5. The subset of AEs considered by the investigator to have a relationship to study drug will be considered to be treatment-related AEs. If the investigator does not specify the relationship of the AE to study drug, then the AE will be considered treatment-related. The incidence of AEs and treatment-related AEs will be tabulated.

Descriptive statistics and mean change from baseline will be determined for quantitative variables (eg, laboratory assessments, vital signs [blood pressure, pulse, respiratory rate, and body temperature]) at each assessment time.

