2.2.2. Safety Endpoints

[figure not shown]
Study subjects will be assessed for the safety and tolerability of ruxolitinib cream throughout the study. Following completion of the treatment period (or the last application of study drug for those who discontinue early), participants will have follow-up assessments 30 (+7) days after the end of treatment to evaluate safety.

The safety endpoints of this study include the following:

- The type, frequency, and severity of treatment emergent AEs (TEAEs).
- Occurrence of serious AEs (SAEs).
- Vital signs
- Clinical laboratory assessments

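### The SAP closes the TEAE window at Week 8 (EOT), while the protocol sets no end date and collects AEs for at least 30 further days; SAP Section 10 does not declare the change

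*SAP*

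**What the plan says.** **Definition of a TEAE**

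- SAP 6.1.7.1 has two arms. The first takes "AEs with onset at the time of or following the start of treatment with IP through Week 8 (EOT"). The second takes AEs that began before treatment and then increased in severity or relationship, with the same end at Week 8 (EOT).
- Protocol 10.4.5: "A TEAE is any AE either reported for the first time or worsening of a pre-existing event after first dose of study drug". There is no end date, and relationship is not mentioned. The section goes on: "Analysis of AEs will be limited to TEAEs, but data listings will include all AEs regardless of their timing to study drug administration".

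**Collection of AEs**

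- Protocol 8.4.1: "Adverse events will be monitored from the time the participant signs the ICF until at least 30 days after the last application of study drug".
- Protocol 8.9.1: "Adverse events and SAEs must be reported up until at least 30 days after the last dose of study drug". It extends this to the date of the "follow-up visit, or until toxicities resolve, return to baseline, or are deemed irreversible, whichever is longer".
- Protocol 9.4 requires SAE reporting up to the last study visit or Day 30 after last application, taking the later.

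**Reporting**

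- SAP 2.2.2: "participants will have follow-up assessments 30 (+7) days after the end of treatment to evaluate safety". It also names the occurrence of SAEs as a safety endpoint, with no TEAE limit.
- SAP 9.1.2 says SAEs are listed and also tabulated by SOC and PT, again with no TEAE limit.
- SAP 13.3 restricts Tables 14.3.1.1 to 14.3.1.6, 14.3.2.1 and 14.3.2.2 to TEAEs. Under SAP 9.1, AEs that are not treatment-emergent appear, flagged, in the listings.
- SAP Section 10 names four changes: the ITT population added, enrollment capped at 47, the STP dropped, and no formal testing of exploratory endpoints.

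**The concern.** Because both documents build the AE summaries on TEAEs, the closing date of the TEAE window decides which events are counted. The SAP moves that date from open-ended to the end of treatment, gives no reason, and does not list the move among its changes. The follow-up period is there for safety, yet an AE that begins in it would reach no incidence table.

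Three outputs are at stake:

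- **Incidence.** If any AE starts or worsens after EOT, the tabulated incidence is lower than under the protocol's definition.
- **Maximum severity.** Protocol 9.3 says "each change in severity will be reported as a separate AE". If that new record is dated at the change, an AE that began on treatment and worsened in follow-up keeps its earlier, lower grade in the severity tables.
- **SAEs.** The SAP promises a tabulation of SAEs, but the planned table would omit those with onset in follow-up.

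The relationship trigger is a second undeclared departure. It can only add events: a pre-treatment AE whose assessed relationship rises becomes a TEAE without having worsened.

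**Working it through.** **1. Reproduce the plan's own day counts.** Inputs are the 56-day treatment period and 30-day follow-up (protocol 4.2) and the target day for the follow-up visit (SAP 6.1.5).

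- Follow-up target day: 56 + 30 = 86, as in SAP 6.1.5.
- Total participation: 42 + 56 + 30 = 128, as in protocol 4.2.

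**2. Share of post-first-dose time outside the SAP window, for a completer.** With EOT on day E and follow-up of F days, the share is F / (E + F). SAP 6.1.5 lets E run from 56 to 63, and the follow-up window lets F run from 30 to 37.

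| E | F | F / (E + F) | Share |
|---|---|---|---|
| 56 | 30 | 30/86 | 34.9% (nominal) |
| 56 | 37 | 37/93 | 39.8% |
| 63 | 30 | 30/93 | 32.3% |
| 63 | 37 | 37/100 | 37.0% |

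**3. Early stopper (illustration, assumed timing).** Last application and ET visit on Day 28, follow-up on Day 58, window closing at the ET visit: 30/58 = 51.7%.

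**4. Weight of one participant.** Assuming all 47 enrolled are in the safety population, one person whose only event of a type begins after EOT changes that incidence by 1/47 = 2.1 percentage points.

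**5. Fate of an AE that starts in follow-up.**

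| Output | Protocol 10.4.5 definition | SAP 6.1.7.1 definition |
|---|---|---|
| Tables 14.3.1.1 to 14.3.1.6 | Counted | Not counted |
| Table 14.3.2.1, if serious | Counted | Not counted, although SAP 9.1.2 sets no TEAE limit |
| AE listing | Listed | Listed and flagged |
| SAE and death listings, if applicable | Listed | Listed |

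**6. A consequence in the schedule.** Protocol Table 4 schedules chemistry and hematology after first dose only at Week 8 and at follow-up. One of those two draws therefore falls after the SAP window. SAP 9.2 summarizes laboratory values at each visit, so the follow-up value would be tabulated, but an AE with onset at that draw would not.

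**The case against.** The best defense is that little depends on this. The study has one arm and 47 enrolled, so no between-arm safety comparison can be distorted. Every AE is listed, non-TEAEs are flagged, and SAEs and deaths have their own listings. An on-treatment window is a legitimate choice, and off-drug events can blur what is seen on drug. All of this stands, and it limits the consequence. It does not answer an undeclared change to a protocol-defined summary, and it supports an additional on-treatment table rather than a silent replacement.

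Three stronger readings are tempting, and the documents do not support them:

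- **That the cut-off is indeterminate for early stoppers**, because SAP 6.1.5 would relabel a Day 28 ET visit as Week 4. Section 6.1.5 assigns visits and measurements, not AE onset dates. Protocol Table 3, protocol 8.9.1 and SAP 3.4 treat Week 8/EOT and ET as one end-of-treatment point. What remains is a wording gap: 6.1.7.1 does not mention ET.
- **That Table 14.3.2.2 is equally affected.** One item in SAP 9.1 speaks of study discontinuation, but the overall summary in 9.1 and the whole of 9.1.1 refer to stopping study drug. An AE that leads to stopping drug must begin or worsen before drug stops, so the cut-off would not remove it.
- **That about a third of AEs would be missed.** The 34.9% is calendar time, mostly off drug, and cannot be read as a share of events.

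**Conclusion.** The point holds as a safety-reporting misalignment worth fixing. The SAP's closing date contradicts the protocol's open-ended definition, and Section 10 declares neither this nor the relationship trigger. As written, AEs that start or worsen in follow-up drop out of the incidence, severity and relationship tables, and follow-up SAEs drop out of the one planned SAE table.

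The excluded time is 34.9% at nominal timing and 32.3% to 39.8% across the visit windows. The effect on incidence cannot be stated without an AE rate, beyond the 2.1 points per participant, which assumes a safety population of 47. The severity effect rests on a further assumption, that severity-change records are dated at the change.

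A reader might infer that safety data are lost or that the trial's conclusions are at risk. Neither follows: all events remain in the listings, and no efficacy analysis uses the TEAE flag.

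**What to change.** - **Closing date.** In both arms of SAP 6.1.7.1, replace the end at Week 8 (EOT) with the later of the last study visit and Day 30 after last application. Protocol 9.4 already uses this period for SAEs. It gives one definite date per participant and covers early stoppers. Pointing only to the collection period in protocol 8.9.1 would not, because that period can run until toxicities resolve.
- **SAE table.** Change the title and filter of Table 14.3.2.1 to match SAP 9.1.2, so that SAEs with onset in follow-up are tabulated.
- **Relationship trigger.** Remove it from the second arm, or declare it in Section 10.
- **Optional supplement.** An on-treatment summary, through the Week 8/EOT or ET visit, may be added beside the main tables.

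The onset rule can stay; it fits the imputation of partial start dates to the first-dose date in SAP 6.1.8.

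**Cost:** one date condition in the TEAE flag, one table's title and filter, and a short amendment to a SAP whose signature record is already complete. Reported AE counts may rise slightly and will include some off-drug events.
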